Table 2 Treatments Administered for Initial and Optional Second Dose..... 23

Table 3 Clinical Laboratory Parameters 28

Protocol Summary

Study Compound: Ubrogепant

Phase: 3

Study Objective: To evaluate the safety and tolerability of intermittent treatment with ubrogепant for the acute treatment of migraine over 1 year

Clinical Hypotheses: Ubrogепant 50 and 100 mg is safe and tolerable for the acute treatment of migraine over 1 year

Study Design

Structure: multicenter, randomized, open-label, 52-week extension study

Duration: 52 weeks

Study Treatment Groups: usual care, ubrogепant 50 mg, or ubrogепant 100 mg

Controls: Not applicable

Dosage/Dose Regimen: Patients randomized to either of the ubrogепant arms will treat up to 8 migraine attacks (of any pain severity) per every 4-week period at home for a total of 1 year. Patients have the option to take a second dose of ubrogепant if the patient has either a nonresponding migraine or a migraine recurrence. The second dose of ubrogепant will be identical to the first dose.

Patients randomized to the usual-care arm will be instructed to treat their migraine with medications that they routinely use to relieve a migraine attack.

[REDACTED]

Study Population Characteristics

Number of Patients: Approximately 1200 patients will be randomized (400 patients per arm) from approximately 200 centers in the United States

Condition/Disease: Migraine with or without aura

Key Inclusion Criteria: To be eligible for study participation, patients must have completed 1 of the lead-in studies, UBR-MD-01 or UBR-MD-02, [REDACTED]

Key Exclusion Criteria: Patients with clinically significant electrocardiogram (ECG), vital sign, physical examination, or laboratory abnormalities, or who require prohibited concomitant medications (see Section 4.5.2)

Response Measures

[REDACTED]

[figure not shown]
Safety: AEs, physical examinations, clinical laboratory determinations, vital sign measurements, ECG parameters, and the Columbia –Suicide Severity Rating Scale (C-SSRS)

[figure not shown]
General Statistical Methods and Types of Analyses:

[figure not shown]
[REDACTED]

The safety analyses will be performed using the Safety population and will include AEs, clinical laboratory evaluations, vital sign measurements, ECG parameters, and the C-SSRS. For each of the clinical, laboratory, vital sign, and ECG parameters, the last nonmissing safety assessment before the first dose in the lead-in study will be used as the baseline for all analyses of that safety parameter. Continuous variables will be summarized by the number of patients and mean, SD, median, minimum, and maximum values. Categorical variables will be summarized by number and percentage of patients.

[REDACTED]

1. Background and Clinical Rationale

What is Migraine and How Prevalent is It?

Migraine affects 18% of women and 6% of men in the United States with a peak prevalence occurring between the ages of 25 to 55 years. Approximately one-third of migraineurs have 3 or more migraine headaches per month, and over half report severe impairment or the need for bed rest during an attack (Lipton 2007). In the United States, work loss due to migraine is estimated to cost ~\$13 billion annually (Hu 1999). Prevalence is similar in Europe, with migraine headache affecting 17.6% of women and 8% of men (Stovner 2010). It is currently ranked by the World Health Organization as 19th among causes of disability (Katsarava 2012).

Migraine is typically characterized by attacks of throbbing, unilateral headache of moderate or severe pain intensity, associated with nausea, vomiting, and/or sensitivity to light (photophobia) and sound (phonophobia). In about 25% of individuals, migraine headache may be preceded by focal neurological dysfunction (aura). Improving the diagnosis and optimizing treatments for migraine have been recognized as critically important to reduce the global burden of migraine (Katsarava 2012).

Because there are no biological markers for migraine, diagnosis is based on clinical history, examination, and the exclusion of other headache disorders. Physicians apply clinical criteria to guide diagnoses and subsequent treatment. Episodic migraine is a syndrome diagnosis applied to patients with migraine (with or without aura) who have 1 to 14 headache days per month. Chronic migraine is a specific International Classification of Headache Disorders criteria, 3rd edition beta version (ICHD-3 beta) diagnosis applied to a subset of patients with ≥ 15 headache days per month (ICHD-3 beta 2013; Katsarava 2012; Olesen 2006).

What is CGRP and Its Relationship to Migraine?

Calcitonin gene-related peptide (CGRP) is a neuropeptide implicated in the pathophysiology of migraine. CGRP levels in the cranial venous outflow (ie, external jugular vein) are increased during a migraine attack (Goadsby 1993) and exogenously administered CGRP has been shown to trigger migraine-like headache in migraineurs. The majority (80 to 90%) of trigeminal A δ fibers that innervate the dura contain CGRP, suggesting that these fibers may be involved in sterile neurogenic inflammation and migraine pain transmission. Furthermore, the CGRP receptor is present on human meningeal and cerebral blood vessels. These observations suggest that activation of the trigeminovascular system, with release of CGRP,

may play a key role in migraine pathogenesis and that inhibition of CGRP function may yield a novel therapeutic approach to treating migraine.

Establishment of CGRP Antagonism to Treat Migraine

The ability of CGRP antagonism to relieve pain in the acute treatment of migraine was established by using an intravenous (IV) formulation of olcegepant (Olesen 2004), and replicated by Merck & Co., Inc., with an oral formulation of telcagepant, a highly selective CGRP receptor antagonist (CGRP RA). In Phase 3 studies, telcagepant was superior to placebo in the primary endpoints of 2-hour pain freedom, 2-hour pain relief, and the absence of associated symptoms (photophobia, phonophobia, and nausea), as well as the key secondary endpoint of 24-hour sustained pain freedom (SPF) (Connor 2009). Serum alanine aminotransferase (ALT) increases were observed with telcagepant, as well as with a second CGRP antagonist, MK-3207. For this reason, the development of these compounds was stopped.

What is Ubrogapant?

Ubrogapant, a novel CGRP receptor antagonist that is chemically distinct from both telcagepant and MK-3207, is now being developed for the acute treatment of migraine. Preclinical and clinical studies conducted to date for ubrogapant have shown no evidence of hepatotoxicity.

A Phase 2b clinical study was conducted, which compared 1, 10, 25, 50, and 100 mg doses of ubrogapant to placebo in the acute treatment of migraine. Overall, all the ubrogapant doses tested were well tolerated and the adverse event (AE) profile of all ubrogapant doses did not differ significantly from placebo. For the primary efficacy endpoint of pain freedom at 2 hours, ubrogapant doses of 1 and 10 mg did not differ from placebo, but doses of 25, 50, and 100 mg were better than placebo. For the primary efficacy endpoint of pain relief at 2 hours none of the ubrogapant doses differed from placebo, probably due to a high placebo response rate.

The absence of migraine-associated symptoms of photophobia, phonophobia, and nausea were assessed as key secondary endpoints. Ubrogapant doses of 50 and 100 mg were significantly better than placebo for absence of phonophobia and photophobia at 2 hours, whereas 25 mg did not differ from placebo. None of the ubrogapant doses differed from placebo for the endpoint of absence of nausea at 2 hours. Measures of sustained migraine headache relief (2 to 24 hours and 2 to 48 hours SPF and sustained pain relief) generally suggested that ubrogapant 50 mg and 100 mg were more effective than the 25 mg dose.

This trial is being conducted to evaluate the long-term safety and tolerability of ubrogepant for the acute treatment of migraine.

The purpose of including the usual-care arm will be to contextualize any safety findings that may occur over the course of a year in the ubrogepant arms. In open-label designs without a comparator arm, it can be difficult to interpret any safety findings that may arise in the experimental treatment arm. The proposed inclusion of the usual-care arm in this study is intended to address this limitation. Because of the stated purpose of the usual-care arm, efficacy data will not be collected from patients randomized to this arm.

2. Study Objectives and Clinical Hypotheses

2.1 Study Objectives

To evaluate the safety and tolerability of intermittent treatment with ubrogepant for the acute treatment of migraine over 1 year.

2.2 Clinical Hypothesis

Ubrogepant 50 and 100 mg is safe and tolerable for the acute treatment of migraine over 1 year.

3. Study Design

This multicenter, randomized, open-label, 52-week extension study will enroll approximately 1200 patients from approximately 200 centers in the United States. Patients will be randomized (1:1:1) to 1 of the following 3 treatment groups: usual care, ubrogepant 50 mg, or ubrogepant 100 mg (400 patients per arm). The study is open-label; however, randomization to the ubrogepant arms (50 and 100 mg) will be blinded. If and when an interim analysis occurs, the doses will be unblinded (see Section 7.6).

Patients randomized to either of the ubrogepant arms will treat up to 8 migraine attacks (of any pain severity) per 4-week period at home for a total of 1 year. Patients have the option to take a second dose of ubrogepant or rescue medication if the patient has either a nonresponding migraine or a migraine recurrence. The second dose of ubrogepant will be identical to the first dose. For detailed information on migraine treatment regimens, including optional second dose and rescue medication, see Section 5.6.

Patients randomized to the usual-care arm will be instructed to treat their migraine with medication(s) that they routinely use to relieve a migraine attack. Their usual medication(s)

for acute treatment will be identified at Visit 1 and any changes throughout the study will be recorded in the electronic case report form (eCRF).

[REDACTED]

The primary outcome is safety and tolerability. The planned safety assessments include collection of AEs, clinical laboratory determinations, ECGs, vital sign measurements, physical examinations, and the Columbia-Suicide Severity Rating Scale (C-SSRS).

3.1 Adjudication Committee and Data Safety Monitoring Board

The Adjudication Charter will be established and will describe the process for the surveillance, monitoring, and adjudication by the Clinical Adjudication Committee of events of post-treatment elevations of ALT and/or aspartate aminotransferase (AST) ≥ 3 times the upper limit of normal (ULN) in the ubrogepant program. The purpose of this committee charter will be to provide a standardized process for the adjudication of data associated with these events in order to determine whether the elevation was due to ubrogepant or not, and to determine whether there was a confounding factor.

An independent Data Safety Monitoring Board will also be established to review safety data and summary reports, identify any safety issues and trends, and make recommendations to the Allergan, including modification or early termination of a trial, if emerging data show unexpected and clinically significant adverse effects of treatment.

4. Study Population and Entry Criteria

4.1 Number of Patients

Approximately 1200 patients will be randomized (400 patients per arm) from approximately 200 centers in the United States.

4.2 Study Population Characteristics

This study will include adult patients with migraine with or without aura who completed Study UBR-MD-01 or UBR-MD-02.

4.3 Inclusion Criteria

To be eligible to participate in the study, patients must meet the following criteria:

1. Written informed consent and patient privacy information (eg, Written Authorization for Use and Release of Health and Research Study Information) obtained from the patient prior to initiation of any study-specific procedures.
2. Completed Study UBR-MD-01 or Study UBR-MD-02.

[Redacted]

4.4 Exclusion Criteria

Patients who meet any of the following criteria will not be eligible to participate in the study:

[Redacted]

2. Requirement for any medication during the study that is on the list of prohibited concomitant medications (see Sections 4.5.2 and 12.2) that cannot be discontinued or switched to an allowable alternative medication.

[Redacted]

[REDACTED]

[REDACTED]

[REDACTED]

[REDACTED]

[REDACTED]

[REDACTED]

[REDACTED]

4.5 Permissible and Prohibited Medications/Treatments

4.5.1 Permissible Medications/Treatments

Medications that are not specifically prohibited are allowed, with the following clarifications and restrictions for patients taking ubrogepant. Note that for patients assigned to the usual-care arm, these restrictions do not apply.

The following medications are allowed during the study but are prohibited within 48 hours prior to taking ubrogepant:

- any triptan
- any ergot derivative
- any opioid
- any nonsteroidal anti-inflammatory drug (NSAID)
- any other form of analgesic (including acetaminophen)
- any antiemetic agent
- any proton pump inhibitor

The following medications are allowed during the study, but are prohibited within 24 hours prior to taking investigational product (IP):

- any antacid
- any H₂ blocker

Examples of allowed but restricted medications listed above are displayed in Section 12.2.

- Aspirin up to 325 mg/day is allowed for cardiac prophylaxis.
- Daily use of pregabalin is allowed.

Patients on a stable prescribed dose of selective serotonin reuptake inhibitors (SSRI) or serotonin norepinephrine reuptake inhibitors (SNRI) in the lead-in study should continue without change in dose throughout this study.

Patients on migraine prophylactic medication (eg, beta-blocker, tricyclic antidepressant, topiramate, valproic acid, botulinum toxin) in the lead-in study should continue without change in dose throughout this study.

Therapy considered necessary for the patient's welfare may be given at the discretion of the investigator. If the permissibility of a specific medication/treatment is in question, please contact Allergan.

4.5.1.1 Acute Treatment/Rescue Medication

Medications for acute treatment of migraine listed above may be taken during the study within the parameters noted in Section 4.5.1 for patients taking ubrogepant. [REDACTED]

[REDACTED]

[REDACTED]

4.5.1.2 Definition of Females of Childbearing Potential and/or Acceptable Contraceptive Methods

For the purposes of this study, females will be considered of childbearing potential unless they are naturally postmenopausal (ie, no menses for 2 years) or permanently sterilized (ie, bilateral tubal ligation, bilateral salpingectomy, bilateral oophorectomy or hysterectomy).

For WOCBP who may participate in the study, the following methods of contraception, if properly used, are generally considered reliable: hormonal contraceptives (ie, oral, patch, vaginal ring, injection, implant), male condom with intravaginal spermicide, diaphragm or cervical cap with spermicide, intrauterine device, vasectomized partner, or sexual abstinence.

For males who may participate in the study, the following methods of contraception, if properly used, are generally considered reliable: postbilateral vasectomy, barrier contraception, or sexual abstinence. Male participants must also refrain from donating sperm during the course of the study.

The investigator and each patient will determine the appropriate method of contraception for the patient during participation in the study.

If a female becomes pregnant during the study, the investigator will notify Allergan immediately after the pregnancy is confirmed, and the patient will be withdrawn from the study after appropriate safety follow-up. The investigator will (1) notify the patient's physician that the patient was being treated with investigational drug ubrogepant, and (2) follow the progress of the pregnancy. The investigator must document the outcome of the pregnancy and provide a copy of the documentation to Allergan.

4.5.2 Prohibited Medications/Treatments

The following medications are prohibited throughout the study period for patients taking ubrogepant. Note that for patients assigned to the usual-care arm, these restrictions do not apply.

- strong and moderate cytochrome P450 3A4 (CYP3A4) inhibitors, including but not limited to: systemic (oral/IV) itraconazole, ketoconazole, fluconazole, erythromycin, clarithromycin, telithromycin, diltiazem, verapamil, aprepitant, cyclosporine, nefazodone, cimetidine, quinine, and human immunodeficiency virus (HIV) protease inhibitors
- strong and moderate CYP3A4 inducers, including but not limited to: barbiturates (eg, phenobarbital and primidone), systemic (oral/IV) glucocorticoids, nevirapine,

efavirenz, pioglitazone, carbamazepine, phenytoin, rifampin, rifabutin, and St. John's wort

- inhibitors of the breast cancer resistance protein (BCRP) transporter (eg, rifampin)
- drugs with narrow therapeutic margins (eg, digoxin, warfarin)

Examples of prohibited medications in the classes noted above are displayed in Attachment [12.2](#).

The decision to administer a prohibited medication/treatment is done with the safety of the study participant as the primary consideration. When possible, Allergan should be notified before the prohibited medication/treatment is administered.

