5.6 Treatment Regimen and Dosing

5.6.1 Ubrogепant

Table 2 presents the treatments that will be administered in this study. Patients randomized to the ubrogепant arms will be instructed to take 2 tablets to treat their migraine attack regardless of the dose group to which they are assigned.

Table 2 Treatments Administered for Initial and Optional Second Dose

Drug/Dose	Dose Frequency	Route of Administration	Investigational Product Administered	
			Initial Dose	Optional Second Dose
Ubrogепant 50 mg	Up to 8 times/4 weeks for 1 year (with optional second dose – maximum 16 times/4 weeks)	Oral (tablet)	Ubrogепant 50 mg/ placebo 50 mg	Ubrogепant 50 mg/ placebo 50 mg
Ubrogепant 100 mg	Up to 8 times/4 weeks for 1 year (with optional second dose – maximum 16 times/4 weeks)	Oral (tablet)	Ubrogепant 50 mg/ ubrogепant 50 mg	Ubrogепant 50 mg/ ubrogепant 50 mg

Patients randomized to the ubrogепant arms will be allowed to treat up to 8 qualifying migraine headaches (of any pain severity) per 4-week period throughout the course of a year. Patients will be instructed to treat the migraine headaches as soon as possible when all of the following conditions are met:

- At least 48 hours since the last dose of ubrogепant
- At least 48 hours of pain freedom (ie, no headache for at least 48 hours)
- The migraine headache started less than 4 hours ago
- The migraine headache is not already resolving on its own
- Prohibited medication has not been taken

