8.7 Compliance with Protocol

All assessments will be conducted at the appropriate visits as outlined in Table 1, and the timing of the visits should occur as close as possible to the specified day. At each visit, the patient will be asked if he or she changed the dose/regimen of any existing concomitant medications or initiated the use of any new concomitant medications since the last visit, to ensure compliance with the protocol.

Patients will record the requested information regarding their migraine attack and ubrogepant taken in the eDiary. Ubrogepant compliance will be closely monitored by counting the number of tablets dispensed and returned. Every effort will be made to collect all unused ubrogepant.

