12.2 Examples of Prohibited Medications

Prohibited Medications

The following medications are prohibited 30 days prior to Screening and throughout the study period for patients taking ubrogepant. Note that for patients assigned to the usual-care arm, these restrictions do not apply.

	Strong/Moderate CYP3A4 Inducers	Strong/Moderate CYP3A4 Inhibitors
Antidepressant/ Antianxiety	Barbiturates 
 • Amobarbital (Amytal[®]) • Aprobarbital (Alurate[®]) • Butalbital (Fiorinal[®], Fioricet[®]) • Butabarbital (Busodium[®], Butisol[®]) • Mephobarbital (Mebaral[®]) • Pentobarbital (Nembutal[®]) • Phenobarbital (Luminal[®], Solfoton[®]) • Secobarbital (Seconal[®]) 	Nefazodone (Serzone [®])
Antiseizure	Carbamazepine (Atretol [®] , Carbatrol [®] , Epitol [®] , Equetro [®] , Tegretol [®]) Oxcarbazepine (Trileptal [®]) Phenytoin (Dilantin [®] , Phenytek [®]) Primidone (Myidone [®] , Mysoline [®])	
Diabetes	Pioglitazone (Actos [®]) Troglitazone (Rezulin [®] , Resulin [®])	
Antiemetic		Aprepitant (Emend [®])
Antihypertension		Diltiazem (Cardizem [®]) Verapamil (Calan [®] , Calan SR [®])
Glucocorticoid (Systemic)	Betamethasone (Celestone [®]) Dexamethasone (Baycadron [®] , DexPak [®]) Hydrocortisone (Cortef [®]) Methylprednisolone (Medrol [®]) Prednisolone (Prelone [®]) Prednisone (Deltasone [®]) Triamcinolone (Kenalog [®])	
Antibiotics	Rifabutin (Mycobutin [®]) Rifampicin/Rifampin (Rifadin [®] , Rifater [®] , Rimactane [®])	Erythromycin (Benzamycin [®] , EryTab [®]) Clarithromycin (Biaxin [®]) Telithromycin (Ketek [®])
Antifungal		Fluconazole (Diflucan [®] , Trican [®]) Itraconazole (Sporanox [®]) Ketoconazole (Nizoral [®])

	Strong/Moderate CYP3A4 Inducers	Strong/Moderate CYP3A4 Inhibitors
Anti-HIV	Efavirenz (Stocrin [®] , Sustiva [®]) Nevirapine (Viramune [®])	Indinavir (Crixivan [®]) Nelfinavir (Viracept [®]) Ritonavir (Norvir [®]) Saquinavir (Fortovase [®] , Invirase [®])
Immunosuppressant		Cyclosporine - oral/intravenous only (Neoral [®] , Sandimmune [®])
Other	St John's wort Enzalutamide (Xtandi [®]) Modafinil (Provigil [®])	Buprenorphine (Cizol [®] , Subutex [®] , Suboxone [®]) Quinine, armodafinil (Nuvigil [™])

Drugs with Narrow Therapeutic Margins	Warfarin (Coumadin [®]) Digoxin (Digitek [®] , Lanoxin [®] , Digox [®]) Cisapride (Prepulsid [®] , Propulsid [®]) Pimozide (Orap [®])
--	---

The following medications are allowed during the study; however, they are prohibited within 48 hours prior to taking ubrogepant:

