Triptan	Almotriptan (Axert [®]) Eletriptan (Relpax [®]) Frovatriptan (Frova [®]) Naratriptan (Amerge [®]) Rizatriptan (Maxalt [®]) Sumatriptan (Imitrex [®]) Zolmitriptan (Zomig [®])
Ergot Derivative	Dihydroergotamine (DHE 45 [®] , Migranal [®]) Ergotamine (Cafergot [®] , Ergomar [®] , Wigraine [®])
Opioid	Tramadol (eg, Ultracet [®] , Ultram [®]) Butorphanol (Stadol [®]) Codeine-containing analgesics (eg, Tylenol with Codeine #3 [®]) Hydrocodone (Zohydro ER [™])/Hydrocodone-containing analgesics (eg, Vicodin [®]) Oxycodone (Oxycontin [®] , Roxicodone [®])/Oxycodone-containing analgesics (eg, Percocet [®]) Morphine (MS Contin [®])
NSAID	Aspirin Combination medicines with NSAIDS (eg, Excedrin [®]) Diclofenac (Arthrotec [®] , Cataflam [®] , Voltaren [®]) Ibuprofen (eg, Advil [®] , Excedrin IB [®] , Motrin [®]) Ketoprofen (eg, Orudis [®]) Naproxen (eg, Aleve [®] , Naprosyn [®])
Analgesic	Acetaminophen (eg, Tylenol [®] or any combination drug Tylenol [®])

Antiemetic agent	Chlorpromazine (Thorazine [®]) Hydroxyzine (Vistaril [®]) Metoclopramide (Reglan [®]) Ondansetron (Zofran [®]) Prochlorperazine (Compazine [®]) Promethazine (Phenergan [®] , Mepergan [®])
Proton Pump Inhibitor	Esomeprazole (Nexium [®]) Lansoprazole (Prevacid [®] , Zoton [®]) Omeprazole (Losec [®] , Prilosec [®] , Zegerid [®]) Pantoprazole (Pantoloc [®] , Pantozol [®] , Protonix [®] , Somac [®] , Zurcal [®]) Rabeprazole (Aciphex [®] , Pariet [®] , Rabecid [®])

The following medications are allowed during the study; however, they are prohibited within 24 hours prior to taking ubrogepant:

Antacid	Aluminum Carbonate Gel (Basaljel [®]) Aluminum Hydroxide (AlternaGEL [®] , Amphojel [®]) Aluminum Hydroxide and magnesium hydroxide (Maalox [®] , Mylanta [®]) Bismuth Subsalicylate (Pepto-bismol [®]) Calcium Carbonate (Alcalak [®] , Quick-Eze [®] , Rennie [®] , Roloids [®] , Titalac [®] , TUMS [®]) Hydrotalcite (Talcid [®]) Magaldrate plus Simethicone (Pepsil [®]) Magnesium Hydroxide (Phillips' Milk of Magnesia [®]) Sodium Bicarbonate (Alka-Seltzer [®] , Bicarbonate of Soda [®])
H₂ Blocker	Famotidine (Pepcid [®]) Nizatidine (Axid [®]) Ranitidine (Zantac [®]) Cimetidine (Tagamet [®])

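### Protocol 4.5.2 bans cimetidine by name for patients taking ubrogepant, while Attachment 12.2 names it as an allowed H2 blocker: 4.5.2 is the better reading, and 12.2 needs a minor correction

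*Protocol*

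**What the plan says.** Protocol 4.5.2 lists drugs that patients taking ubrogepant may not use at any time in the study. Its first group is strong and moderate CYP3A4 inhibitors, and the named examples end with "nefazodone, cimetidine, quinine, and human immunodeficiency virus (HIV) protease inhibitors". The section refers to Attachment 12.2 for further examples of the prohibited classes.

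Attachment 12.2 has a prohibited table and two tables of drugs that are allowed with a restriction. The last of these is introduced by "The following medications are allowed during the study; however, they are prohibited within 24 hours prior to taking" ubrogepant, and its H2-blocker row includes "Cimetidine (Tagamet". The CYP3A4 inhibitor column of the prohibited table does not list cimetidine.

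Section 4.5.1 begins: "Medications that are not specifically prohibited are allowed, with the following clarifications and restrictions for patients taking" ubrogepant. It then lists the restricted classes, among them all H2 blockers with a 24-hour limit, and says that 12.2 shows examples of those restricted drugs.

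None of these restrictions applies to the usual-care arm.

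**The concern.** One named drug has two statuses for the same patients: never allowed, and allowed outside a pre-dose window. Sites apply these lists directly when they advise patients. A coordinator who checks the attachment finds cimetidine by brand name under an allowed heading and has no reason to look further. Outside the window, that site would permit a drug that the main text bans as a CYP3A4 inhibitor.

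The uncertainty may also reach the dosing rule. Section 5.6.1 lets a patient treat an attack only if, among other conditions, "Prohibited medication has not been taken". Whether cimetidine counts for that condition depends on which list is used.

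**Working it through.** No arithmetic beyond a count applies. The check sets the lists side by side.

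**1. Is the text current?** Yes. Both entries are in the protocol body and its attachment, not in an amendment summary, and neither is affected by redaction.

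**2. When do the entries disagree?**

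| Time of cimetidine use | 4.5.2 | 12.2, H2-blocker row |
|---|---|---|
| Within 24 hours before a ubrogepant dose | Barred | Barred |
| More than 24 hours before a dose | Barred | Allowed |
| After a dose, with no further dose in the next 24 hours | Barred | Allowed |

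The third line carries its condition because 5.6.3 permits a second dose 2 to 48 hours after the first, and the 24-hour rule looks back from that dose too.

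**3. Is this a pattern or a single slip?** Section 4.5.2 names these CYP3A4 inhibitors individually: itraconazole, ketoconazole, fluconazole, erythromycin, clarithromycin, telithromycin, diltiazem, verapamil, aprepitant, cyclosporine, nefazodone, cimetidine and quinine. That is 13, plus HIV protease inhibitors as a class.
- In the inhibitor column of 12.2: all except cimetidine, so 13 − 1 = 12. The HIV class is represented by four drugs.
- In an allowed row of 12.2: cimetidine only, 1 of 13.

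Aprepitant is the closest parallel. It is an antiemetic, and antiemetics as a class are allowed with a 48-hour limit. Attachment 12.2 puts "Aprepitant (Emend" in the inhibitor column and leaves it out of the allowed antiemetic row. Cimetidine did not get the same treatment.

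**4. Does the text resolve it?** Largely, by inference. The allowed rows of 12.2 illustrate 4.5.1. The permission in 4.5.1 covers only drugs that are not specifically prohibited. Section 4.5.2 specifically prohibits cimetidine. An example should not reach further than the permission it illustrates, so 4.5.2 should prevail. The protocol does not state this, and a reader of 12.2 alone does not see the limit.

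**5. What follows for dosing?** The 5.6.1 condition gives no look-back period and cites neither list. Take cimetidine used 30 hours before an attack, as an illustration. Under the 12.2 row that use is permitted. Under 4.5.2 it is not, but whether it blocks the dose depends on a look-back that 5.6.1 does not give.

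**The case against.** The strongest reply is that this is a stray entry in a list of examples, that the body text settles it, and that controls exist. Section 8.7 has each visit include a medication query ("the patient will be asked if he or she changed the dose/regimen of any existing concomitant medications", or started new ones). Section 4.5.1 refers doubtful drugs to the sponsor, and 4.5.2 asks for the sponsor to be told, when possible, before a prohibited drug is given. Most of this stands, and it limits the weight of the point. It does not remove the error: the queries detect use without saying whether it is allowed, and referral helps only a site that sees a doubt.

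A reader might infer more than the documents support:
- *That two rules of equal rank compete with nothing to choose between them.* The link from 4.5.1 to 12.2 favours 4.5.2.
- *That the absence of cimetidine from the prohibited column is itself a contradiction.* The attachment gives examples only, so an omission proves nothing. The conflict lies in naming the drug as allowed.
- *That the H2-blocker class wording in 4.5.1 is a second contradiction.* It can be read as yielding to 4.5.2. It is unclear, not contradictory.
- *That eligibility turns on which list is read.* Exclusion criterion 2 covers "Requirement for any medication during the study that is on the list of prohibited concomitant medications (see Sections 4.5.2 and 12.2"), so a drug banned in 4.5.2 is already within it. It applies only if the drug cannot be stopped or replaced, and the same 12.2 row offers three other H2 blockers: famotidine, nizatidine and ranitidine.
- *That a dose taken 30 hours after cimetidine is definitely barred under 4.5.2.* Section 5.6.1 does not say so.

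**Conclusion.** The inconsistency is real and minor. It concerns one drug and one row of an attachment and, for use during the study, only the ubrogepant arms. The consequence that clearly stands is that a site using 12.2 alone would permit cimetidine outside the pre-dose window. A carry-over into the 5.6.1 dosing condition is possible. The number of patients affected is unknown, because the documents give no rate of cimetidine use.

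A reader might also infer that the safety results are at risk. They are not. The Safety population (SAP 5.1.1.1.1) depends on dosing or randomization, not on concomitant medication; the safety summaries are descriptive; and concomitant medications are summarized and listed whatever their status (SAP 5.1.1.2.8). The label could matter in classifying deviations, but SAP 5.1.1.2.3 leaves those definitions to a separate specification, not available here, which may already settle the question.

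The view that 12.2 holds the slip rests on the link in 4.5.1 and on the consistent handling of the other 12 named inhibitors. The sponsor's intention is not stated.

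**What to change.** In Attachment 12.2, remove cimetidine from the H2-blocker row and list it in the strong/moderate CYP3A4 inhibitor column, as is done for aprepitant. In 4.5.1, add the words *except cimetidine* to the H2-blocker bullet. The heading over that column of 12.2 also imposes a restriction for the 30 days before Screening, so the sponsor should confirm that this is meant to apply.

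If the sponsor intends to allow cimetidine outside the 24-hour window, delete it from 4.5.2 and leave 12.2 as it is. Either way, apply the same single rule when classifying deviations.

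The cost is one drug name moved and two words added, by clarification letter or with the next amendment. Amendment 1 made edits of this kind: it moved proton pump inhibitors from the 24-hour list to the 48-hour list and added armodafinil to 12.2. Neither the design nor any analysis changes.
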